2.11 Replacement of Subjects

Replacement of subjects who have withdrawn or been withdrawn from the study will be allowed to be replaced with prior approval from the sponsor and/or IRB.

2.12 Schedule of Visits and Procedures

	Visit #1*	Visit #2	Call	Visit #3	Visit #4
Procedure	Screening and Pre-treatment Procedures	Device Use	Phone Call 1 Week Post Device Use (1-10 Days)	Follow Up 30 Days Post Device Use (+/- 1 Week)	Follow Up 90 Days Post Device Use (+/- 1 Week)
Medical History	X				
Pregnancy Verification	X	X			
Informed Consent	X				
Photographs (2D and/or 3D)	X	X		X	X
MyEllevate Procedure		X			
Parameters		X			
Treatment Discomfort/ Pain Evaluation		X			
Subject Diary		X		X	X
Subject Satisfaction Questionnaire				X	X
PG AIS				X	X

SGAIS				X	X
Adverse Events Assessment	X	X	X	X	X

*Screening and Pre-treatment Procedures may occur at the same time as the Device Use visit.

2.13 Evaluation Methods

Photographs:

Photographs (2D and/or 3D) will be taken at baseline and at the 30 and 90 day follow up visit to assess the efficacy and safety of treatment. 2D photography may be taken at any time during the procedure to document performance and/or adverse events.

Treatment Discomfort/Pain Evaluation:

Subjects will be asked to report the general level of treatment discomfort on a scale of 0 (none) to 10 (maximum intolerable pain) using the universal pain assessment tool (Appendix B)

Physician and Subject Questionnaire:

The Global Aesthetic Improvement Scale (GAIS) ranging from “worse” to “very much improved” will be used to judge the improvement as seen by the subject and Investigator.

Global Aesthetic Improvement Scale Assessment	
Rating	Description
1	Very Much Improved- Optimal cosmetic result in this subject
2	Much Improved- Marked improvement in appearance from the initial condition, but not completely optimal for this subject.
3	Improved- Obvious improvement in appearance from initial condition, but a re-treatment is indicated.
4	No Change- The appearance is essentially the same as the original condition.
5	Worse- The appearance is worse than the original condition.

Subject Questionnaire:

The subject will be asked their level of satisfaction using a 6-point Likert scale that ranges from “extremely satisfied” to “extremely unsatisfied.”

Subject Satisfaction	
Rating	Description
6	Extremely Satisfied
5	Satisfied
4	Slightly Satisfied
3	Slightly Unsatisfied
2	Dissatisfied
1	Extremely Unsatisfied

Blinded Evaluation:

Three blinded independent reviewers will perform a photographic evaluation in which they will be asked to identify pre-treatment images when compared to post treatment images. The reviewers

will be Board Certified Dermatologists, Surgeons, and/or trained professionals and will be chosen based on availability and have relevant clinical experience. They will attend a training session prior to grading.

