2.14 Adverse Event Recording

All data captured must be supported by the Investigator's timely assessment and documentation of the adverse event in the case report forms or source documents. All documented adverse events will be reviewed by the Sponsor or designee to determine whether the adverse event meets regulatory reporting requirements and to ensure timely adverse event reporting to meet local and global regulatory requirements. All adverse events must be followed until their resolution.

Adverse Events Pertaining to the MyEllevate® Procedure:

Mild discomfort during treatment may be experienced by the subject. Anticipated side effects include pain, edema (swelling) and erythema (redness), bleeding, bruising, and limitations in opening mouth.

Other possible side effects may include; dimpling, infection, poor wound healing, facial asymmetry, hematoma (fluid accumulation), numbness or other changes in skin sensation, temporary or permanent hair loss along incisions, scarring, burns (up to 3rd degree), tissue hardness, weakness of the lower lip, skin irregularities, skin discoloration, suture surfacing, deep venous thrombosis with cardiac or pulmonary sequelae, facial nerve paresis of the mandibular bands.

Adverse Events Pertaining to Anesthetic:

Pain and numbness may be experienced at the site of the injection. Other side effects may include redness, blanching, swelling, application site reaction, rash, infection, skin damage or nerve damage at the site of the injection. Temporary loss of sensation and muscle function at the site of injection, although uncommon, may also be experienced.

1% lidocaine (Lidocaine) with Epinephrine Injection

Lidocaine with epinephrine contains the preservative sodium metabisulfite which may cause allergic-type reactions including anaphylactic symptoms such as itching, hives, swollen areas of the body, and/or trouble breathing and life-threatening or less severe asthmatic episodes in certain susceptible people. If the subject has a reaction, medical attention may be provided or they may need to seek emergency care.

Adverse Events Pertaining to the Surgical Marker:

Using surgical marker has minimal risks and may produce effects on the body such as redness or a rash. Markings may remain visible for a few days or may be removed with alcohol.

Other Cautions:

Incomplete response or no response may occur since some subjects may not respond to treatment.

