2.15 Statistical Analysis

2.15.1 Hypothesis

For this study to be considered a success, the side effect profile is acceptable to the Physician as it relates to this type of treatment.

For the additional assessments to be considered a success, the following must be true:

- Subject satisfaction will be $\geq 80\%$
- In cases where the subject's improvement is being graded on a scale, such as the GAIS scale, we will test the statistical significance of our results against a hypothetical population that would have no change (average score of 4).
- Correct identification of pre-treatment images when compared to post treatment (90 day) images will be $\geq 80\%$.
- Subject diaries are collected.

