2.15.2 Sample Size Rationale

Based on the need for data collected from this study, it was determined that a total of 10 subjects will be required, including departures.

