2.15.5 Analysis of Efficacy Variables

Additional efficacy variable is the change from baseline to Visit 4 (90 day follow up visit).

Baseline is defined as the last assessment prior to the first treatment. The change from baseline to visits 3 and 4 will be analyzed using a Mixed Model Repeated Measures Analysis of Variance. A pairwise treatment group comparison at visit 4 will be performed using the results of this analysis. If a patient has no post-baseline assessment of the primary efficacy variable it will be assumed that the change from baseline to visit 4 is zero. The changes to visits 3 and 4 will be left as missing. Statistical significance with respect to the treatment group comparison at visit 4 will be declared if the two-sided p-value is < 0.05 . For each treatment group, summaries will be prepared for both the observed assessment and the change from baseline. The summaries will include the sample size,

mean, median, standard deviation, minimum, and maximum. The statistical significance of the mean change from baseline for each treatment group will be determined using a paired t-test.

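### The only blinded efficacy measure asks which photograph is pre-treatment, not which looks better, so it can show visible change but not improvement

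*Combined protocol and SAP*

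**What the plan says.** Section 2.13 describes the reading: "Three blinded independent reviewers will perform a photographic evaluation", in which "they will be asked to identify pre-treatment images when compared to post treatment images". Section 2.15.1 sets the pass mark: "Correct identification of pre-treatment images when compared to post treatment (90 day) images will be" at least 80%. Section 1.2 lists this evaluation among the optional assessments and mentions both the 30-day and the 90-day images.

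Section 2.14 lists possible side effects that could be seen in a photograph, among them "dimpling, infection, poor wound healing, facial asymmetry", and further on scarring, discoloration and surfacing sutures.

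The GAIS in section 2.13 includes a category for a worse appearance, but it "will be used to judge the improvement as seen by the subject and Investigator". The blinded reviewers do not complete it.

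On size, section 2.15.2 says only that "it was determined that a total of 10 subjects will be required, including departures". The plan does not say how the three reviewers' answers are combined, whether the 80% is taken over subjects or over readings, who is in the denominator, how many images are shown together, or what rate guessing would give.

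**The concern.** A reviewer who spots a scar or a dimple and concludes that the image is post-treatment has answered correctly. The score does not separate that answer from one based on a better jawline, so a subject who looks worse can count toward an efficacy criterion.

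This matters because every other efficacy rating comes from the subject or the Investigator in a study that section 2.2 describes as open label. Section 2.3 adds that employees of the Investigator will take part. The photograph reading is the one measure protected from those sources of bias, and as written it cannot support a statement that appearance improved.

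A second question is whether just reaching 80% differs from guessing. The plan leaves open the choices that decide it.

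**Working it through.** **Direction.** Set side by side, section 2.13 asks for identification only, section 2.15.1 scores identification only, and section 2.14 lists visible marks that aid identification. An illustration with 10 subjects (invented counts, not a forecast):

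- 6 subjects improved and correctly identified
- 2 subjects not improved but identified by a procedure mark
- 2 subjects not identified

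Identification rate = (6 + 2)/10 = 80%, a pass. Improvement rate = 6/10 = 60%. The documents give no rate of visible marks at 90 days, so the real gap cannot be estimated.

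**Guessing.** The plan gives no calculation behind its 10 subjects, so there is no figure of its own to reproduce. Inputs: 10 subjects (section 2.15.2), three reviewers (section 2.13), 80% (section 2.15.1). Assumptions, not in the plan: one majority call per subject and two images per pair, so guessing is right half the time. A majority of three guesses is also right half the time: (3 + 1)/8 = 0.5.

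For 8/10:

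- One-sided p = [C(10,8) + C(10,9) + C(10,10)]/2^10 = (45 + 10 + 1)/1024 = 0.0547.
- Two-sided p = 2 × 0.0547 = 0.109.
- Exact (Clopper-Pearson) 95% CI: the lower limit L solves P(X ≥ 8 | 10, L) = 0.025 and the upper limit U solves P(X ≤ 8 | 10, U) = 0.025. This gives 44.4% to 97.5%, which includes 50%.

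The lowest subject-level count that reaches 80% with fewer evaluable subjects, and the next count up with 10:

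| Result | One-sided p | Two-sided p |
|---|---|---|
| 6/7 | 8/128 = 0.0625 | 0.125 |
| 7/8 | 9/256 = 0.0352 | 0.070 |
| 8/9 | 10/512 = 0.0195 | 0.039 |
| 8/10 | 56/1024 = 0.0547 | 0.109 |
| 9/10 | 11/1024 = 0.0107 | 0.021 |

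If the 80% is instead taken over 10 × 3 = 30 readings, the mark is 24/30. To allow for three people reading the same pair, I used a beta-binomial for each subject's three readings with mean 0.5 and within-subject correlation ρ (both shape parameters equal to 0.5(1 − ρ)/ρ), summed over 10 subjects. The two-sided p is twice the upper tail:

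| ρ | Two-sided p for 24/30 |
|---|---|
| 0 | 0.0014 |
| 0.5 | 0.026 |
| 0.7 | 0.043 |
| 0.8 | 0.055 |
| 1 | 0.109 |

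If the 30-day and 90-day images were shown together with the pre-treatment image, guessing would be right one time in three, and 8/10 would give a one-sided p of 0.0034.

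**The case against.** The best defence on direction is that section 2.15.1 requires all the additional criteria together. Satisfaction must also reach 80%, and GAIS is to be tested against no change. Scars and dimpling are also adverse events and fall under the primary safety objective. That much stands: a reader might infer that visible harm alone could make the additional assessments a success, and the documents do not support this. It does not answer the point, because those other ratings are unblinded and cannot lend direction to the blinded one.

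It can also be said that reviewers might take the worse-looking image to be pre-treatment, so that harm would count as an error. Some may. Nothing in the plan tells them to, and a scar or a surfacing suture points the other way. The score would still mix improvement with recognition.

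On guessing, the objection is stronger. The assessment is optional, 80% is a descriptive mark, and the plan claims no test against chance. A reader might infer that the criterion fails a significance level that the plan sets for it. It does not. The two-sided 0.05 appears for group comparisons of baseline variables (section 2.15.4) and for a different analysis in section 2.15.5: "Statistical significance with respect to the treatment group comparison at visit 4 will be declared if the two-sided p-value is < 0.05".

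**Conclusion.** The directional point holds without any statistical assumption. The one blinded efficacy measure can show that something visible changed, but not that it changed for the better. This should be corrected. It does not touch the primary safety objective.

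The guessing point is secondary and conditional. With one majority call per subject, two images per pair and all 10 subjects evaluable, just meeting 80% does not exclude guessing. A reader might go further and infer that an 80% result can never be told apart from chance. The figures do not support that: 8/9 excludes 50% at the two-sided 5% level, and so does 24/30 unless readings within a subject correlate at about 0.8 or more. What can be said is that the same 80% may or may not exclude guessing, depending on a unit, a denominator and a display that the plan does not state.

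**What to change.** Keep the identification task and the three reviewers, and make these changes before reading starts:

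- Show each pre-treatment and 90-day pair in random order without labels. Before naming the pre-treatment image, each reviewer says which looks better: A, B or no difference. Asking this first matters, because a reviewer who has just named one image as the earlier one will be inclined to favour the other.
- Base any blinded claim of improvement on the proportion of subjects for whom at least two of the three reviewers prefer the 90-day image. Report the identification rate as evidence of visible change only.
- Take the subject as the unit (majority of three), state who is in the denominator, and give exact 95% CIs for both rates.
- Set the 50% guessing rate beside the identification rate only. It does not apply to the preference rate, where no difference is an allowed answer, nor to any composite of the two.

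Raising the pass mark to 9/10 is not a substitute. It would exclude guessing under the assumptions above, but it would still lack direction, and a true identification rate of 80% would pass only 10 × 0.8^9 × 0.2 + 0.8^10 = 37.6% of the time.

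The cost is one extra item on the reading form and a line in the reviewers' training, with no extra subjects, visits or readers. The downside is that the blinded improvement rate may be lower than the identification rate.

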2.14 Adverse Event Recording

All data captured must be supported by the Investigator's timely assessment and documentation of the adverse event in the case report forms or source documents. All documented adverse events will be reviewed by the Sponsor or designee to determine whether the adverse event meets regulatory reporting requirements and to ensure timely adverse event reporting to meet local and global regulatory requirements. All adverse events must be followed until their resolution.

Adverse Events Pertaining to the MyEllevate® Procedure:

Mild discomfort during treatment may be experienced by the subject. Anticipated side effects include pain, edema (swelling) and erythema (redness), bleeding, bruising, and limitations in opening mouth.

Other possible side effects may include; dimpling, infection, poor wound healing, facial asymmetry, hematoma (fluid accumulation), numbness or other changes in skin sensation, temporary or permanent hair loss along incisions, scarring, burns (up to 3rd degree), tissue hardness, weakness of the lower lip, skin irregularities, skin discoloration, suture surfacing, deep venous thrombosis with cardiac or pulmonary sequelae, facial nerve paresis of the mandibular bands.

Adverse Events Pertaining to Anesthetic:

Pain and numbness may be experienced at the site of the injection. Other side effects may include redness, blanching, swelling, application site reaction, rash, infection, skin damage or nerve damage at the site of the injection. Temporary loss of sensation and muscle function at the site of injection, although uncommon, may also be experienced.

1% lidocaine (Lidocaine) with Epinephrine Injection

Lidocaine with epinephrine contains the preservative sodium metabisulfite which may cause allergic-type reactions including anaphylactic symptoms such as itching, hives, swollen areas of the body, and/or trouble breathing and life-threatening or less severe asthmatic episodes in certain susceptible people. If the subject has a reaction, medical attention may be provided or they may need to seek emergency care.

Adverse Events Pertaining to the Surgical Marker:

Using surgical marker has minimal risks and may produce effects on the body such as redness or a rash. Markings may remain visible for a few days or may be removed with alcohol.

Other Cautions:

Incomplete response or no response may occur since some subjects may not respond to treatment.

2.15 Statistical Analysis

2.15.1 Hypothesis

For this study to be considered a success, the side effect profile is acceptable to the Physician as it relates to this type of treatment.

For the additional assessments to be considered a success, the following must be true:

- Subject satisfaction will be $\geq 80\%$
- In cases where the subject's improvement is being graded on a scale, such as the GAIS scale, we will test the statistical significance of our results against a hypothetical population that would have no change (average score of 4).
- Correct identification of pre-treatment images when compared to post treatment (90 day) images will be $\geq 80\%$.
- Subject diaries are collected.

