2.0 PROTOCOL

2.1 Protocol Methodology and Analysis

Methodology:

Subjects are to be enrolled in this clinical study if they are a healthy male or female between the age of 18 – 65. Up to 10 subjects will be enrolled at 2 study centers. All subjects will attend a screening/pre-procedure visit which may be performed on the same day as the procedure visit but no more than 30 days prior to their procedure. Subjects will receive a phone call 1 week (1-10 days) after their procedure to record side effects. Subjects will return for follow up visits at 30 and 90 days post their procedure for efficacy and side effects assessments.

An unscheduled visit or phone call may be performed at any time during the study at the request of the subject or as deemed necessary by the site Investigator.

Analysis:

Upcoming generations are proving to have an interest in aesthetic treatments and will drive demand for innovated products, procedures, and practice design.ⁱ Due to this shift in patient base, practices need to evolve to adapt to the newer generational ideologies. There have been rapid advances in minimally invasive neck rejuvenation over the past few years and using innovative procedure offers great promise to our aging population. The MyEllevate® procedure used for soft tissue approximation and elevation of sub dermis and underlying muscle of the submentum and jawline needs to be further investigated to collect additional data to support the safety and efficacy of the procedure.

Relevance:

According to the 2020 Plastic Surgery Statistics Report, neck lifts are in the top 10 cosmetic surgical procedures performed, with over 160,000 surgeries performed despite the average 8.1 weeks most surgeons stopped performing elective surgical procedures for due to the COVID-19 pandemic.ⁱⁱ There was also a survey conducted by American Society of Plastic Surgeons (ASPS) during the pandemic which found that 11% of women surveyed indicated they are more interested in cosmetic plastic surgery or non-surgical procedures now than before COVID-19.ⁱⁱⁱ Currently, the comparable procedures and/or treatments available for visible platysma bands, glands and/or sagging in the submentum, jawline and/or neck include, but not limited to, NeckTite and a neck lift. The limitations of current products on the market include different side effect profiles and how invasive the procedure is.

Testability:

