2.15.3 Patient Populations

Interim results may be collected and reported. All data will be analyzed at the end of the study. The primary analysis will be performed by the intention-to-treat approach. Everyone who begins the treatment is part of the study whether he or she completes the study or not. The most appropriate method of handling missing values will be chosen based on the individual trial goals, endpoints and context.

The analysis of demographic, medical history, and efficacy variables will be based on all patients who are randomized and receive at least one treatment. The analysis of safety data will be based on all patients who receive at least one treatment, and have at least some safety data.

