3.2 Risk Management

The Investigator in this clinical trial has been invited to participate based on his/her previous experience with the use of the system and/or similar systems and industry experience. Experience with treatments is the most critical element in managing subject risk in this trial.

In addition, as with any study, there is a risk of bias. Objective evaluation methods may be used in conjunction with subjective evaluation methods when feasible. The value of the compensation to the clinical investigator for conducting the study is not influenced by the study outcome. If photographic results are listed as the primary objective, they are to be evaluated by blinded evaluators who did not partake in the study. If information concerning investigator assessment of improvement or investigator satisfaction is collected, then it is not listed as an objective for the study.

All other known risks will be disclosed to the subject via the informed consent process. Since this is an elective procedure and the subjects are volunteers, it can be assumed that their signature on the informed consent is indicative of their agreement to accept the risks involved.

The risks to the subjects who participate in this study are the same as those for the subject undergoing similar non-ablative radiofrequency treatment. It is possible to have an adverse reaction to the MyEllevate® procedure. There may be some side effects that we don't know about yet.

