4.0 DEVICE DESCRIPTION AND SPECIFICATIONS

Device Name	Date of 510(k)	Indication(s):
ICLED Surgical Suture System	09 October 2009 K091061	Indicated for soft tissue approximation and elevation of sub dermis and underlying muscle of the submentum & jawline

The ImplicitCare ICLED Surgical Suture System provides a minimally invasive means of performing reconstructive, plastic and cosmetic surgery procedures by eliminating the need for extensive subdermal undermining through a large incision. Rather, the suture is guided subcutaneously using rigid rods like blunt-tipped needles. The ICLED Surgical Suture System, is a sterile, single use device kit consisting of five (5) device components:

- 1.) Marking Tape: Intended to locate the marking sites of suture insertion. The backing of the tape is a medical acrylic adhesive
- 2.) Lancet: Intended to puncture the skin at the site of suture insertion. The Lancet creates a perforation just large enough to pass the Suturod™ and suture.
- 3.) Clearing Device: Intended to sweep away any dermal attachments for a 360° radius around the skin puncture made by the Lancet. This helps prevent “dermal tethering” as the suture is passed.
- 4.) Suturod™: Stainless steel, connected at the midpoint by a 100” (254 cm) length of USP 4-0 (1.5 Metric) TEVDEK® II braided nonabsorbable polyester Suture. The suture, acquired directly from Teleflex, is coated with polytetrafluoroethylene (PTFE) for improved handling characteristics and to reduce “tissue drag,” and is green in color.
- 5.) Light Tool (Handle): Contains an LED light source supplied by three (3) 1.55V silver oxide batteries, and which connects to the Suturod™. When connected, the light created by the LED passed through the fiber optic light pipe within the Suturod™ and Illuminates the distal tip. This permits visual verifications—through the dermis—of both the path and depth of the Suturod™ as it passed through the subdermal tissue.

Device Description	Device Image
Lancet: consists of a 400 series stainless steel blade in a polycarbonate handle.	

Device Description	Device Image
Clearing Device: right angled 300 series stainless steel rod 0.078" in diameter extending from the distal end of a polycarbonate handpiece.	
Suturod™ Rod: The Suturod™ is 0.078" in diameter, 8.5" long, is composed of 300 series stainless steel, and is hollow, with a fiber optic light pipe running the length of the Suturod™ internally.	

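### The only study-level success criterion is an unnamed Physician's opinion of the side effects, with no failing adverse-event result, no reference rate and no rule if the two centers' investigators disagree

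*Combined protocol and SAP*

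**What the plan says.** Section 1.2 makes safety, through adverse-event collection, the primary objective. Section 2.15.1 then sets one condition for the study as a whole: "the side effect profile is acceptable to the Physician as it relates to this type of treatment". The same section gives two of the additional assessments a countable threshold of at least 80% (subject satisfaction and photographic identification at 90 days).

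Section 2.14 lists effects without frequencies. The list starts with "Anticipated side effects include pain, edema (swelling) and erythema (redness), bleeding, bruising, and limitations in opening mouth" and extends, among other possible effects, to "deep venous thrombosis with cardiac or pulmonary sequelae". Section 14.0 defines and collects relatedness, severity on three grades, seriousness and outcome. Section 2.15.6 reports number and percent per outcome and makes no comparisons.

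On setting and timing, section 2.1 states "Up to 10 subjects will be enrolled at 2 study centers". Section 2.15.3 says "All data will be analyzed at the end of the study" but also allows interim results to be collected and reported, and section 5.0 lets the sponsor ask for intermediate data after each visit. Section 2.15.3 defines one safety set: treated patients with some safety data.

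**The concern.** The primary objective has a success condition that cannot be applied from the text. Three elements are missing.

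- **A failing result.** No event type, grade, seriousness category or count is marked as unacceptable, although the data needed for such a rule are collected under section 14.0.
- **A reference.** The condition is relative to a type of treatment, but no adverse-event rate is given for any treatment. Section 2.1 says only that earlier studies of the procedure found complications to be few.
- **A decision-maker.** The Physician is singular and undefined, and there are two centers.

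Two careful readers of the same adverse-event table could therefore reach opposite verdicts and both be following the plan. At stake is the statement that the study succeeded on safety. Section 2.1 wants the data in order to confirm safety, and section 3.3 concedes that the safety profile is uncertain. A verdict with no prespecified basis cannot carry that weight.

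**Working it through.** **1. What can be reproduced.** Section 2.15.2 gives 10 subjects, including departures. No rate, margin, alpha, power or precision target stands behind that number, so it can be neither reproduced nor contradicted. For the same reason the error rates of the success criterion cannot be computed.

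**2. The reference, side by side.** Section 3.2 is the one place that equates this study's risks with those of another treatment; it says they "are the same as those for the subject undergoing similar non-ablative radiofrequency treatment". Section 4.0 describes a different kind of device, in which "the suture is guided subcutaneously using rigid rods like blunt-tipped needles". The two sections must be reconciled before the phrase about type of treatment has a meaning. Neither gives a rate.

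**3. What the sample can exclude.** This measures the precision behind any safety statement, not the defect in the criterion. Input: n = 10 (sections 2.1 and 2.15.2). For zero events, the exact two-sided 95% upper limit is 1 − 0.025^(1/n) and the one-sided limit is 1 − 0.05^(1/n). For x > 0 the Clopper-Pearson limits are the 0.025 quantile of Beta(x, n − x + 1) and the 0.975 quantile of Beta(x + 1, n − x).

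| Subjects with event / n | Two-sided 95% interval |
|---|---|
| 0/10 | 0 to 30.8% |
| 1/10 | 0.3% to 44.5% |
| 2/10 | 2.5% to 55.6% |
| 0/8 (n assumed) | 0 to 36.9% |

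The one-sided upper limit for 0/10 is 1 − 0.05^(1/10) = 25.9%. The chance of seeing at least one event in 10 subjects, 1 − (1 − p)^10, is 9.6%, 18.3%, 40.1% and 65.1% at assumed true rates of 1%, 2%, 5% and 10%.

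Treated subjects who leave stay in the analysis, because section 12.0 keeps data collected before withdrawal. The safety set falls below 10 through under-enrolment, through departure before treatment without replacement (section 2.11), or if a treated subject has no safety data. The last is unlikely, since section 2.12 schedules an adverse-event assessment at the device-use visit.

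**4. Why the decision-maker matters.** Illustration only. Assume 5 subjects per center, and that each investigator accepts the profile only if none of their own 5 has a given event.

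- True rate 10%: each accepts with probability 0.9^5 = 0.590. Both accept: 0.9^10 = 34.9%. At least one accepts: 1 − (1 − 0.590)^2 = 83.2%.
- True rate 20%: each accepts with probability 0.8^5 = 0.328. Both accept: 0.8^10 = 10.7%. At least one accepts: 1 − (1 − 0.328)^2 = 54.8%.

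The documents give neither the split nor the acceptance rule. The example shows only that the unstated choice between both and either can more than double the chance of a success claim.

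**The case against.** The strongest reply is that a 10-subject, open-label, descriptive study of a cleared device needs no formal test, and that clinical judgement is normal in safety review. Both points are right, and the preferred fix below imposes no test. They do not justify declaring success on a basis that was never stated.

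Several stronger readings are tempting, and the documents do not support them.

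- *Success is assured whatever the data show.* It is not. A Physician can find the profile unacceptable; the criterion is subjective, not impossible to fail.
- *The two centers' data are not combined.* Section 2.15.3 defines a single safety set, so the data are pooled by implication. What is missing is whose judgement counts.
- *The protocol sets several competing safety benchmarks.* Section 2.1 names alternatives that "include, but not limited to, NeckTite and a neck lift", but as a list of what is available, not as a benchmark for risk. Section 4.0 is a device description. Only the mismatch between the risk statement in section 3.2 and the device in section 4.0 stands.
- *The judgement is fixed at the end of the study.* Sections 2.15.3 and 5.0 allow interim data to be seen and reported, so the opinion could form sooner.

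It is also fair to say that rates may exist elsewhere. Section 3.3 says data from prior investigations will be used, and section 24.0 lists predicates and a retrospective protocol on the same device. Those sources, the Instructions for Use, and sections 7.0 and 8.0 were not available here. The statement that no reference rate or named judge is given applies to the available text only.

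Finally, number and percent with n shown let a reader compute intervals. That is true, but printing them costs little and keeps a low count from being read as reassurance.

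**Conclusion.** The point holds as a gap in prespecification. In the available text, the number of adverse-event results defined as failing is 0, the number of reference rates is 0, and the Physician is not identified. The success verdict would be an opinion that can be formed after data, including interim data, have been seen.

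The consequence is limited to the safety claim. A reader might infer that the safety data or their collection are compromised, or that a treatment or regulatory decision hangs on the verdict. The documents support neither: event collection is well defined in section 14.0, no action is attached to success, and section 2.1 states that the device is already cleared. The change should still be made, because safety is the primary objective and even a clean result in 10 subjects leaves true rates up to about 31% (two-sided) or 26% (one-sided) compatible with the data. Those limits assume 10 subjects in the safety set and are higher with fewer.

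**What to change.** **Section 2.15.1.** Replace the success sentence with: *Safety is the primary objective and will be reported descriptively; no success criterion is set for the side effect profile.* Add that meeting the criteria for the additional assessments does not make the study a success on safety. Without that addition, the only success criteria left in the section would belong to assessments that section 1.2 calls optional.

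**If the sponsor keeps a success claim.** Before enrolment, fix three things: a countable rule built on the relatedness, severity, seriousness and outcome data already collected; the reference procedure, with sections 3.2 and 4.0 reconciled; and who applies the rule across both centers, including what happens on disagreement. The threshold is the sponsor's choice.

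**Section 2.15.6.** Add: *For adverse events (any, by type, by severity, related, serious), the number of subjects with the event over the number treated with safety data will be reported with exact (Clopper-Pearson) 95% CIs; pain scores will be summarized descriptively.* The restriction to adverse events avoids an interval for every value of the 0 to 10 pain scale. State also that 0/10 has a two-sided 95% upper limit of about 31% (one-sided about 26%), higher if fewer than 10 are in the safety set.

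**Cost.** A few sentences and a few exact intervals, with no new data or visits. The downside is a less favourable claim, no success criterion for the primary objective, and slightly more reporting.
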